### **Product Quality Complaints for Janssen Medicinal Products**

A PQC may have an impact on the safety and efficacy of the product. Timely, accurate, and complete reporting and analysis of PQC information from studies are crucial for the protection of patients, investigators, and Janssen Scientific Affairs, and are mandated by regulatory agencies worldwide. Janssen Scientific Affairs has established procedures in conformity with regulatory requirements worldwide to ensure appropriate reporting of PQC information. Lot and/or Batch #s shall be collected or any reports of failure of expected pharmacological action (i.e., lack of effect).

All initial PQCs involving a Janssen product under study must be reported to Janssen Scientific Affairs by the Sponsor Investigator within 24 hours after being made aware of the event.

If the defect for a Janssen product under study is combined with either a serious adverse event or non-serious adverse event, the Sponsor Investigator must report the PQC to Janssen Scientific Affairs according to the serious adverse event reporting timelines. A sample of the suspected product should be maintained for further investigation if requested by Janssen Scientific Affairs.

### **Maintenance of Safety Information**

All safety data should be maintained in a clinical database in a retrievable format. The Institution and Sponsor Investigator shall provide all adverse events, both serious and non-serious, in report format. However, in certain circumstances more frequent provision of safety data may be necessary, e.g. to fulfill a regulatory request, and as such the data shall be made available within a reasonable timeframe at Janssen Scientific Affair's request.

### **Transmission Methods:**

The following methods are acceptable for transmission of safety information to Janssen Scientific Affairs:

- Electronically via Janssen SECURE Email service (preferred)
- For business continuity purposes, if SECURE Email is non-functional:
  - Facsimile (fax), receipt of which is evidenced in a successful fax transmission report
- Telephone (if fax is non-functional).

Please use the contact information and process information provided by Janssen Scientific Affairs.

## **Procedures for Reporting Adverse Events (AE), Serious Adverse Events (SAE), Pregnancy, and Product Quality Complaints (PQC) to Janssen Scientific Affairs**

### **A. AEs, SAEs, Special Situations and Pregnancy Reporting.**

The Institution and the Sponsor Investigator will transmit SAEs and Special Situations in a form provided by Janssen Scientific Affairs in accordance with Section VIII Transmission methods, in English within 24-hours of becoming aware of the event(s).

All available clinical information relevant to the evaluation of a related SAE or Special Situation is required.

- The Institution and/or Sponsor Investigator are responsible for ensuring that these cases are complete and if not are promptly followed-up. A safety report is not considered complete until all clinical details needed to interpret the case are received. Reporting of follow-up information should follow the same timeline as initial reports.
- Copies of any and all relevant correspondences with regulatory authorities and ethics committees regarding any and all serious adverse events, irrespective of association with the Janssen Product under study, are to be provided to Janssen Scientific Affairs using a transmission method in Section VIII within 24 hours of such report or correspondence being sent to applicable health authorities.

### **B. PQC Reporting**

The Institution and the Sponsor Investigator will report any suspected PQC to the Janssen contact within 24 hours of becoming aware of the complaint. The product should be quarantined immediately and if possible, take a picture.

#### **Reconciliation of SAEs**

At a minimum, on a quarterly basis and at the end of the Study, Janssen Scientific Affairs will provide to the Institution and/or Sponsor Investigator, a listing of all SAEs reported to Janssen Scientific Affairs. The Sponsor Investigator will review this listing and provide any discrepancies to Janssen Scientific Affairs.

Upon request, Institution and/or Sponsor Investigator shall provide Janssen Scientific Affairs with a summary list of all SAEs, and AEs of Special Interest and Special Reporting Situation reports to date, for reconciliation purposes.

**Dissemination of Safety Information from Janssen Scientific Affairs to Institution/Sponsor Investigator** Sponsor Investigator will be responsible for submitting IND safety reports for the Study Product to Institution's IRB in accordance with Federal regulations 21 CFR 312.66.

Janssen Scientific Affairs agrees to provide to the Sponsor Investigator IND safety reports for the Study Product as they become available until all subjects in the Protocol have completed their last Study visit according to the Protocol (i.e. Last Subject Last Visit has occurred).

### **Other Safety Considerations**

Any significant worsening noted during interim or final physical examinations, electrocardiograms, x-rays, and any other potential safety assessments, whether or not these procedures are required by the protocol, should also be recorded as a nonserious or serious AE, as appropriate, and reported accordingly.

**12. Data Safety Monitoring Board (DSMB)** A DSMB consisting of individuals with expertise in each of the efficacy areas (anti-coagulation therapy, atrial fibrillation, and cardiac CT), as well as in anti-coagulation trials and statistics will be established. The PI will prepare interim reports to the DSMB on a regular basis, every 6 months or more often as it deems appropriate. Reports that include general study information such as accrual, dropout, and ineligibility rates and other performance parameters, will be available to the study leadership and will be discussed with them at open sessions. Data relating to safety and efficacy that are presented by treatment arm will be considered highly confidential and will be available only to the DSMB and the statistician preparing the reports, and will be discussed at closed sessions of the DSMB. The DSMB will have an initial meeting prior to the opening of the study to review the report format and content proposed by the PI and determine if they are satisfactory or need to be modified. Interim reports to the DSMB will focus on analyses of the safety data -- primarily bleeding -- but other safety-related outcomes, such as CT related adverse effects, will also be reviewed in an unblinded fashion. The DSMB will decide on the basis of these data and the stopping boundaries whether to recommend modifying or stopping the trial and will make recommendations to the sponsor and the study leadership. A copy of the DSMB minutes and reports will be provided to Janssen as well.

## **13. STATISTICAL CONSIDERATIONS**

### Statistical analysis

All analyses will be performed on a full analysis set basis (those who stay in the trial to the follow up scan). For the primary analysis, ITT (defined as all those randomized into the study) will be used. Continuous variables will be expressed as mean and standard deviation; categorical variables expressed as absolute numbers and percentages. Baseline variables will be compared with an independent t-test (two tailed) after performing Levene's test for equality of variances in all normally distributed continuous variables and the Mann-Whitney test (two-tailed) in all not normally distributed variables. Categorical variables will be tested with two-sided Fisher's exact test. An analysis of variance (ANOVA) model with treatment as the main effect will be used to compare the treatment effect of rivaroxaban and warfarin treatment

strategies. For all measures, the analysis of covariance (ANCOVA) model controlling for baseline demographics and baseline CACS values will be performed. Treatment groups also will be compared with respect to incidence rates of adverse events, laboratory abnormalities, bleeding rates, and concomitant medication use. Measurements and change from baseline in coronary artery calcium scores, vital signs (blood pressure and pulse rate), continuous laboratory variables and compliance values will be summarized using descriptive statistics (mean, standard deviation, minimum, median and maximum) by treatment groups and visit. If the interaction of treatment by baseline laboratory values or CACS is significant at the 0.10 level or below, the nature of the interaction will be further explored. Spearman's rank correlation coefficient will be used for testing correlation between the mean Agatston score. All parameters showing a significant univariate relation with an increased coronary Agatston score and those representing a plausible mechanism in terms of calcification [age, VKA duration, left atrium (LA) diameter, statins, angiotensin-converting enzyme (ACE)-inhibitors] will be included as covariates in a logistic regression model (retention level set at 0.1), odds ratios and 95% confidence intervals (CIs) calculated, and results checked for interaction.

Statistical analysis will be performed with SPSS statistical software (SPSS, Inc. release 18.0) and statistical significance assumed for  $P < 0.05$ . The primary and secondary efficacy analyses will include all patients who undergo randomization (intention-to-treat population) and include all events from the time of randomization until the end of the study. The analyses of bleeding events will include all patients who receive at least one dose of a study drug and included all events from the time the first dose of a study drug was received until 2 days after the last dose is received.

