### Study Endpoints

Events will be recorded. Stroke will be defined as a focal neurologic deficit, from a nontraumatic cause, lasting at least 24 hours and categorized as ischemic (with or without hemorrhagic transformation), hemorrhagic, or of uncertain type (in the case of patients who do not undergo brain imaging or in whom an autopsy is not performed). The rate of myocardial infarction, hospitalization for angina and revascularization will be recorded. The primary safety outcome will be major bleeding, defined, according to the ISTH criteria, as clinically overt bleeding accompanied by a decrease in the hemoglobin level of at least 2 g per deciliter or transfusion of at least 2 units of packed red cells, occurring at a critical site, or resulting in death. Additional safety outcome will be clinically relevant nonmajor bleeding, defined as clinically overt bleeding that does not satisfy the criteria for major bleeding and that led to hospital admission, physician-guided medical or surgical treatment, or a change in antithrombotic therapy. Other safety measures will include any bleeding, other adverse events, and liver-function abnormalities.

The primary and secondary efficacy and safety measures will be adjudicated on the basis of prespecified criteria by a clinical-events committee whose members will be blinded to the study-group assignments.

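### Completers are the only stated analysis set for non-bleeding adverse events and laboratory abnormalities, so patients who die or leave before the 12-month scan are left out of those comparisons

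*Combined protocol and SAP*

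**What the plan says.** Four statements in section 13 (Statistical analysis) bear on who is analysed.

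- The default: "All analyses will be performed on a full analysis set basis (those who stay in the trial to the follow up scan". This is followed at once by an exception: "For the primary analysis, ITT (defined as all those randomized into the study) will be used".
- The safety comparisons, in the same paragraph and with no set of their own: "Treatment groups also will be compared with respect to incidence rates of adverse events, laboratory abnormalities, bleeding rates, and concomitant medication use".
- Efficacy, further on: "The primary and secondary efficacy analyses will include all patients who undergo randomization (intention-to-treat population". These analyses are to "include all events from the time of randomization until the end of the study".
- Bleeding, in the next sentence: "The analyses of bleeding events will include all patients who receive at least one dose of a study drug", counting events "until 2 days after the last dose is received".

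Under Study Endpoints, major bleeding is the primary safety outcome and clinically relevant non-major bleeding is an additional one. The list ends: "Other safety measures will include any bleeding, other adverse events, and liver-function abnormalities". Stroke, myocardial infarction, hospitalisation for angina and revascularisation are to be recorded, but they are not labelled as efficacy or safety.

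**The concern.** Staying in the trial to the 12-month scan is something that happens after randomisation and may depend on treatment. A patient who dies before month 12 cannot meet the condition, and neither can one who leaves because of, say, a hypersensitivity reaction or liver injury. These are the patients whom an adverse-event comparison most needs to count.

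The trial is open label, and only one arm changes drug at randomisation. Early intolerance and early exit could therefore differ between arms. If they do, the completers in the two arms are no longer comparable groups, and the adverse-event table no longer describes the patients who were randomised.

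**Working it through.** **Step 1. Match each planned analysis to the set that the text gives it.**

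| Analysis | Set stated | Where in Statistical analysis |
|---|---|---|
| Primary endpoint | All randomised | Exception directly after the default; repeated in the efficacy sentence |
| Secondary efficacy | All randomised | Efficacy sentence; conflicts with the default |
| Bleeding, including major bleeding | At least one dose, to 2 days after the last dose | Bleeding sentence; the default paragraph also lists bleeding rates |
| Stroke, MI, angina hospitalisation, revascularisation | Not explicit; the efficacy sentence speaks of all events and may cover them | Efficacy sentence |
| Non-bleeding adverse events and SAEs | Completers | Default only |
| Laboratory and liver-function abnormalities | Completers | Default only |

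Only the last two rows have nothing but the completer rule. The rule turns on leaving the trial, not on stopping the drug: a patient who stops treatment but returns for the scan is kept. Laboratory samples are planned at 0, 6 and 12 months, so an abnormal month-6 result in a patient who leaves at month 8 would be collected but not compared.

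**Step 2. How many patients could be missing.** The Study Design text plans 120 enrolled and at least 100 available at the end. The design paragraph just before it gives 110 enrolled. No dropout rate is stated, so there is no plan figure to reproduce independently. I take patients available for final analysis to be those who reach the scan, and I carry the figure of 100 over to the 110 case.

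- 120 − 100 = 20; 20/120 = 16.7%.
- 110 − 100 = 10; 10/110 = 9.1%.

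**Step 3. Effect on incidence (assumed inputs).** Suppose 10 of 100 completers have a given type of event, so the completer rate is 10.0%. With 20 leavers, of whom k had the event, the all-patient rate is (10 + k)/120.

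| k of 20 | All-patient rate | Understatement, 1 − 10.0%/rate |
|---|---|---|
| 2 | 12/120 = 10.0% | 0% |
| 5 | 15/120 = 12.5% | 20% |
| 10 | 20/120 = 16.7% | 40% |
| 15 | 25/120 = 20.8% | 52% |

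There is no bias when leavers have events at the completers' rate (k = 2). With 110 enrolled and 5 of 10 leavers affected, the rate is 15/110 = 13.6%, an understatement of 26.7%.

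**Step 4. Effect on the arm difference (assumed inputs).** Take 60 per arm, with 15 leavers on rivaroxaban and 5 on warfarin, so 45 and 55 completers. The same share of leavers has had an event in each arm.

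No true difference, 12/60 in each arm (20%):

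| Leavers with event | Completer rates | Difference |
|---|---|---|
| 0 of 15, 0 of 5 | 12/45 = 26.7% vs 12/55 = 21.8% | +4.8 points |
| 3 of 15, 1 of 5 | 9/45 = 20.0% vs 11/55 = 20.0% | 0 |
| 6 of 15, 2 of 5 | 6/45 = 13.3% vs 10/55 = 18.2% | −4.8 points |
| 12 of 15, 4 of 5 | 0/45 = 0% vs 8/55 = 14.5% | −14.5 points |

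True difference of +10.0 points, 15/60 against 9/60: with 12 of 15 and 4 of 5 leavers affected, completers show 3/45 = 6.7% against 5/55 = 9.1%, a difference of −2.4 points. With no leavers affected they show 15/45 = 33.3% against 9/55 = 16.4%, or +17.0 points.

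With equal losses of 10 and 10 and 12/60 events per arm, the completer difference stays at 0. If 5 leavers per arm had events, however, both rates fall from 20% to 7/50 = 14%.

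**The case against.** The strongest reply is that the main safety outcome is not affected. The bleeding sentence is specific and should displace the general default. Major bleeding is then analysed in everyone with at least one dose, and a fatal bleed within the dosing window is kept. The mention of bleeding rates in the earlier paragraph names a comparison, not a second bleeding population. I accept this; what remains for bleeding is a wording conflict. A reader might infer that every analysis other than the primary is on completers, bleeding included. The efficacy and bleeding sentences contradict that.

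A second reply is that little can be hidden. Section 10 makes any death a serious adverse event, section 11 requires all adverse events to be recorded in the CRF, vital status is sought for patients who leave, and the DSMB reviews safety by arm with no restriction to completers. This is correct for collection and monitoring. A reader who infers that deaths vanish from the safety evaluation goes too far. But none of these provisions sets the denominator of the final between-arm comparison.

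A third reply concerns direction and size. It is tempting to say that the bias runs towards no harm and no difference. Step 4 shows that it can run either way. A striking example can be built: 5 completer events per arm plus event-related exits of 12 against 2 give 17/60 against 7/60 (two-sided Fisher P = 0.039), while completers show 5/48 against 5/52 (P = 1.0). That needs all 12 exits in one arm, but only 2 of 8 in the other, to be event-related. With 10 against 4 the all-patient comparison is 15/60 against 9/60, P = 0.25. The loss of significance is a product of the chosen split and should not be cited as the expected effect.

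It may also be said that full analysis set was meant in its usual, wider sense. The plan's own parenthesis rules that out.

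**Conclusion.** The plan is wrong as written on one defined group of comparisons: non-bleeding adverse events and SAEs (deaths from non-bleeding causes among them), and laboratory and liver-function abnormalities. For these, the completer rule is the only one stated, and it excludes patients because of what happened to them after randomisation.

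The planned figures allow up to 16.7% (20 of 120) or 9.1% (10 of 110) of randomised patients to be omitted. Those percentages assume that the retention target is met and refers to the scan. The effect on the results cannot be estimated, because the documents give neither reasons for exit nor losses by arm; the figures in Steps 3 and 4 are illustrations only. They support two statements. Incidence is understated if leavers have more events than completers, and unequal losses can hide or create a difference between arms.

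This should be corrected, but it is not among the most serious kinds of fault: the primary safety outcome has its own treated-patient set, efficacy is assigned to all randomised patients, and the excluded safety data will have been collected.

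**What to change.** In the Statistical analysis section:

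1. Limit the completer set to supportive analyses of the imaging endpoints.
2. State that all comparisons of adverse events, serious adverse events, deaths, and laboratory and liver-function abnormalities include all randomised and treated patients by arm, whether or not they reach the 12-month scan.
3. State that the bleeding rates listed with the other safety comparisons use the population given later in the section for bleeding events.
4. State explicitly that stroke, myocardial infarction, angina hospitalisation and revascularisation are analysed in all randomised patients.
5. When defining treated patients, say what counts as the first dose of study drug in the warfarin arm, whose patients are already on treatment at randomisation.

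The cost is a change of wording. No new data are needed, since section 11 already requires every adverse event to be recorded. Reported incidences may be somewhat higher than in completers, and laboratory summaries will need to show how many patients contribute at each visit.

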### Sample Size

**Sample Size Estimation.** Sample sizes for each efficacy area have been calculated assuming performance of two-sided 0.05 level tests and 90% power for the primary endpoint and >85% power for the secondary endpoint to detect differences considered clinically meaningful and plausible based on prior studies. We have based sample sizes on at least 90% power in all end points because false negatives could lead to abandoning further study of a treatment that could have a major positive impact on myocardial infarction in this population. The primary endpoint is progression of atherosclerosis after 1 year of treatment with warfarin compared to rivaroxaban as measured by the annualized relative change in the coronary calcium score, as assessed by the Agatston score. The primary endpoint will be the percentage change in CAC from the baseline, which was calculated as follows:  $(CAC \text{ score at 1 year} - CAC \text{ score at baseline}) / CAC \text{ score at baseline} \times 100$ . From multiple 1 year randomized studies in [name] lab, the mean annualized relative change in the Agatston calcium score was  $27.2 \pm 9.5\%$  and on pilot-treatment group, we observed an average change of  $7.5 \pm 4\%$ . Given a 19.7 % annual change difference (27.2% vs. 7.5%) between two groups was observed from primary data, the trial requires 100 in total (50 patients per arm) to attain power of 90% to detect the effect size according to a two-tailed two-sample t-test at a significance level 0.05 (see figure). If we consider the secondary

endpoint (noncalcified plaque volume change), we will have >85% power without drop-off at a two-tailed significance level 0.05 with 120 subjects.

The secondary endpoint is noncalcified plaque volume, using cardiac CTA. Cardiac CTA has been used successfully by [name] to measure progression of atherosclerosis (30-32). In one relevant study, the mean annualized relative change in the non-calcified plaque volume among 62 subjects given statin was -0.037 with a standard deviation of 0.351. This secondary comparison has power of 0.80 to detect an effect size of 0.5, the mean difference in the annualized relative change in the non-calcified plaque volume between the rivaroxaban and warfarin, according to a two sample t-test at a two-tailed significance level 0.05.

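### The efficacy models assume one common variance while the planning spreads differ between groups; an unequal-variance method should be named in advance (minor, conditional on unequal completer numbers)

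*Combined protocol and SAP*

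**What the plan says.** The Statistical analysis section (Section 13) names two efficacy models. For the main comparison: "An analysis of variance (ANOVA) model with treatment as the main effect will be used to compare the treatment effect" of the two strategies. For all measures: "the analysis of covariance (ANCOVA) model controlling for baseline demographics and baseline CACS values will be performed". With two arms, the first is the pooled-variance t-test. Neither model carries a provision for unequal variances.

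Unequal variance is mentioned once, for baseline data: "Baseline variables will be compared with an independent t-test (two tailed) after performing Levene's test for equality of variances".

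The Sample Size section gives the outcome inputs. The annualised relative change in Agatston score is 27.2 ± 9.5% from earlier one-year studies, "and on pilot-treatment group, we observed an average change of" 7.5 ± 4%. The test is described as "according to a two-tailed two-sample t-test at a significance level 0.05 (see figure"), again without saying whether variances are pooled.

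Allocation is 1:1. The Study Design section expects at least 100 analysable patients from 120 and gives no split of the losses by arm. Its opening item gives enrolment as 110. The Statistical analysis section names both the patients with a follow-up scan and all randomised patients as the analysis set, and states no method for missing scans.

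**The concern.** The variance check sits where it is least needed. Randomisation already gives the arms the same baseline distribution in expectation. The 12-month change is where the planning figures suggest different spreads, and there the models assume a single variance.

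Pooling is safe while the arms have equal numbers. The trial is open label, one arm switches drug and the other does not, and about 20 patients are expected to be lost, so unequal completer numbers are possible. If the more variable arm ends up smaller, the pooled standard error is too small: intervals are too narrow and p-values too low. If it ends up larger, the reverse holds. The protocol's conclusions present this trial as a pilot that could lead to an outcome study, so the precision attached to its estimate matters as well as the p-value.

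**Working it through.** **Inputs.**
- Sample Size: difference 19.7 points; spreads 9.5 (taken as warfarin) and 4 (taken as rivaroxaban), read as SDs; two-sided 5%. SD ratio 9.5/4 = 2.4; variance ratio 90.25/16 = 5.6.
- Other spreads for 12-month CAC change in the Background: 18.5 (placebo) and 9.4 (treated) in the 23-patient garlic-extract trial, SD ratio 1.97; 36 (untreated) and 28 (treated) in the 149-patient statin study, SD ratio 1.29.
- Completers: 100 of 120, split unknown. With 60 randomised per arm and 20 lost, 40/60 is the extreme. With 110 enrolled and 10 lost, it is 45/55.

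**The plan's own figure.** The average-variance SD is √((9.5² + 4²)/2) = 7.29, so the standardised difference is 19.7/7.29 = 2.70. A two-sample t-test then reaches 90% power with 5 per arm (power 0.89 at 4, 0.96 at 5), not the stated 50. Fifty per arm at 90% power implies an SD near 19.7/[√(2/50) × (1.960 + 1.282)] = 30.4. The stated size is therefore not reproduced from the stated spreads, which limits how much weight they can bear.

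**Error of the pooled test.** In large samples the two-sided error is 2 × [1 − Φ(1.96 × R)], where R is the ratio of the pooled to the true standard error.

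At 40 warfarin / 60 rivaroxaban:
- pooled variance (39 × 90.25 + 59 × 16)/98 = 45.55
- pooled SE² = 45.55 × (1/40 + 1/60) = 1.898
- true SE² = 90.25/40 + 16/60 = 2.523
- R = √(1.898/2.523) = 0.867, giving an error of 8.9%

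At 60/40:
- pooled variance (59 × 90.25 + 39 × 16)/98 = 60.70
- pooled SE² = 60.70 × (1/60 + 1/40) = 2.529
- true SE² = 90.25/60 + 16/40 = 1.904
- R = 1.153, giving an error of 2.4%

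At 50/50 the two standard errors coincide and the error is 5.0%.

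Simulation with normal data (1,000,000 trials per split) gives:

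| Warfarin / rivaroxaban completers | Pooled, SDs 9.5 and 4 | Pooled, SDs 18.5 and 9.4 | Pooled, SDs 36 and 28 | Welch |
|---|---|---|---|---|
| 60 / 40 | 2.5% | 2.8% | 4.0% | 5.0% |
| 55 / 45 | 3.7% | 3.8% | 4.5% | 5.0% |
| 52 / 48 | 4.5% | 4.6% | 4.8% | 5.0% |
| 50 / 50 | 5.1% | 5.1% | 5.0% | 5.0% |
| 48 / 52 | 5.8% | 5.7% | 5.2% | 5.0% |
| 45 / 55 | 6.9% | 6.5% | 5.6% | 5.0% |
| 40 / 60 | 9.0% | 8.3% | 6.2% | 5.0% |

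The same percentages are the miss rates of the nominal 95% interval when the means do differ, because the statistic centred on the true difference has the same distribution whatever that difference is.

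**Equal SDs.** With the same SD in both arms, the pooled test gives 5.0% at both 60/40 and 40/60.

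**Power.** At a difference of 19.7 with SDs 9.5 and 4, power is about 1.00 at 50/50, 60/40 and 40/60, for both the pooled and the Welch test.

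**ANCOVA.** With three assumed noise covariates and SDs 9.5 and 4 (20,000 trials per split), ordinary standard errors gave 6.9% at 45/55 and 8.7% at 40/60. HC3 standard errors gave 4.7% and 4.9%, and 4.4% at 60/40.

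**The case against.** Several points on the other side stand.

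- **The spreads belong to the alternative.** The 9.5 and 4 come with means of 27.2 and 7.5. If the two drugs acted identically on CAC, both arms would share one distribution and the pooled test would hold its level at any split. Inflation of the test itself needs equal means with unequal spreads, which no passage suggests. What survives is the interval: when the means differ, its coverage is still wrong if spreads and completer numbers both differ.
- **Direction and size.** The error exceeds 5% appreciably only if the more variable arm loses more patients. The 9% needs all 20 losses in warfarin. If 20 of 120 are lost without regard to arm (an assumption), a split of 45/55 or worse against warfarin has a probability of about 1.3%, and the error averaged over splits is about 5.2%.
- **Weak inputs.** The spreads do not reproduce the sample size and do not come from a stated rivaroxaban–warfarin comparison. The ± sign may not always mean an SD. For the garlic-extract plus coenzyme Q10 trial in the Background, 32 ± 6 versus 58 ± 8 gives 26/√(6² + 8²) = 2.6, p = 0.009, close to the reported 0.01 if these are standard errors. If 9.5 and 4 were standard errors, the variance ratio could not be recovered without group sizes.
- **Intention to treat.** An analysis of all randomised patients would keep the arms near equal. This helps only if patients without a 12-month scan are given a value, and no method for that is stated. Naming the ITT set does not settle the matter.

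A reader might infer that the 5% level fails as soon as completer numbers differ, or that power is at risk. The documents support neither: 52/48 and 48/52 give 4.5% and 5.8%, and power at the planned effect is near 1.00 either way.

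**Conclusion.** The concern holds as a minor, conditional weakness. The efficacy models have no provision for unequal variances, and the planning figures, together with two studies cited in the Background, show more spread in the faster-progressing group. If the spreads are as in the Sample Size section and completer numbers are unequal, the nominal 5% could be anywhere from about 2.5% to 9%, depending on which arm loses patients. With the statin study's spreads the range narrows to 4.0% to 6.2%. With equal completers or equal variances there is no problem.

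This rests on reading 9.5 and 4 as SDs, assigning the larger to warfarin, about 100 completers, and normally distributed percentage change. The last is uncertain, since a baseline CAC score as low as 10 is admitted and percentage change may be skewed; skewness was not simulated.

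**What to change.** In the Statistical analysis section, state in advance that the unadjusted comparison uses Welch's t-test, and that the ANCOVA of CAC change and of the plaque volumes uses heteroscedasticity-robust standard errors (for example HC3). Apply both unconditionally, with no variance pretest on the outcome. Levene's test on baseline variables then plays no part in the efficacy analysis.

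The cost is one sentence, written before outcome data by arm are seen. If the variances are in fact equal, the loss of efficiency is negligible. HC3 may be slightly conservative, as the 4.4% at 60/40 shows. The change does not resolve how missing 12-month scans are handled, which needs its own statement.
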